| Incisional/core biopsy of tumor | X (1 month to 1 day prior to first cetuximab) | | X (any time during this interval) | | | | | X (within 2 months) |
| Biopsy of skin | X (1 month to 1 day prior to first cetuximab) | | X (any time during this interval) | | | | | |
| CBC, differential, platelets | X (within 1 month to 1 day prior to enrollment) | X | | X | | | | |
| Serum Chemistries ² | X (within 1 month to 1 day prior to enrollment) | X | | X | X (monthly for two times +- 2 weeks) | X (within 1 month) | | |
| Liver Enzymes ³ | X (within 1 month to 1 day prior to enrollment) | | X | | | | | |
| Pregnancy Test ⁴ | X (within 1 month to 1 | | | | | | | |

| | day prior to enrollment) | | | | | | |
|---------------------------------------|--------------------------|--|------------------------------|--|--|--------------------------------------|---|
| Radiographic Assessments ⁵ | X ⁵ | | X (CT neck w IV contrast) | | | X (PET/CT at 3 months +- 1 month) | X |

1. To include toxicity assessment, ECOG performance status, weight
2. Includes: Electrolytes, including serum magnesium, potassium, Calcium, BUN, Creatinine, Glucose,
3. Includes: Total and Direct. Bilirubin, AST/ALT, Alkaline Phosphatase, Albumin, Total Protein.
4. Women 18-55 who have not undergone menopause must have urine pregnancy test within 3 weeks of enrollment.
5. Radiographic assessment prior to enrollment will consist of PET/CT obtained no more than 2 months prior to enrollment. CT neck w IV contrast will be obtained within 2 weeks to 1 day prior to first dose of cetuximab.
6. Assessment of rash
7. Any time during that week

7. Treatment Plan

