7.4.3.5 Non-Hematologic Toxicity

See above

Cardiopulmonary Arrest

Cardiopulmonary arrest and/or sudden death occurred in 4 (2%) of 208 patients treated with radiation therapy and Erbitux as compared to none of 212 patients treated with radiation therapy alone in a randomized, controlled trial in patients with SCCHN. Three patients with prior history of coronary artery disease died at home, with myocardial infarction as the presumed cause of death. One of these patients had arrhythmia and one had congestive heart failure. Death occurred 27, 32, and 43 days after the last dose of Erbitux. One patient with no prior history of coronary artery disease died one day after the last dose of Erbitux. Carefully consider use of Erbitux in combination with radiation therapy in head and neck cancer patients with a history of coronary artery disease, congestive heart failure, or arrhythmias in light of these risks. Closely monitor serum electrolytes, including serum magnesium, potassium, and calcium, during and after Erbitux.

Pulmonary Toxicity

Interstitial lung disease (ILD), including 1 fatality, occurred in 4 of 1570 (<0.5%) patients receiving Erbitux in clinical trials. Interrupt Erbitux for acute onset or worsening of pulmonary symptoms. Permanently discontinue Erbitux for confirmed ILD.

Dermatologic Toxicity

Dermatologic toxicities, including acneform rash, skin drying and fissuring, paronychial inflammation, infectious sequelae (for example *S. aureus* sepsis, abscess formation, cellulitis, blepharitis, conjunctivitis, keratitis, cheilitis), and hypertrichosis occurred in patients receiving Erbitux therapy. Acneform rash occurred in 76–88% of 1373 patients receiving Erbitux in clinical trials. Severe acneform rash occurred in 1–17% of patients.

Acneform rash usually developed within the first two weeks of therapy and resolved in a majority of the patients after cessation of treatment, although in nearly half, the event continued beyond 28 days. Monitor patients receiving Erbitux for dermatologic toxicities and infectious sequelae. Instruct patients to limit sun exposure during Erbitux therapy.

Hypomagnesemia and Electrolyte Abnormalities

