In patients evaluated during clinical trials, hypomagnesemia occurred in 55% of patients (199/365) receiving Erbitux and was severe (NCI CTCAE Grades 3 and 4) in 6–17%. The onset of hypomagnesemia and accompanying electrolyte abnormalities occurred days to months after initiation of Erbitux. Periodically monitor patients for hypomagnesemia,

hypocalcemia, and hypokalemia, during and for at least 8 weeks following the completion of Erbitux. Replete electrolytes as necessary.

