7.5.6 Adherence/Compliance

Patients will receive cisplatin q 3 weeks or weekly per their medical oncologist. They should adhere to their oncologist's recommendations (based on the protocol) re administration of cisplatin. Failure to do so may result in removal from the study.

8. Toxicity Monitoring and Adverse Event Reporting

All patients who receive one dose of protocol therapy will be evaluable for assessment of toxicity. Prior to each cycle the treating physician will fully assess the patient's condition with respect to possible treatment related toxicities. All adverse events, whether observed by the physician or reported by the patient, occurring during the active portion of therapy, or up to 30 days after the last dose of treatment will be graded by a numerical score according to the NCI's Common Terminology Criteria for Adverse Events (CTCAE), Version 4.0 (<http://ctep.cancer.gov/reporting/ctc.html>) and recorded in the patient's medical record. Grade 2 and above toxicities will be recorded.

For the purposes of reporting laboratory abnormalities, only Grade 3-4 adverse events will be recorded on the adverse event CRF pages. Grade 1-2 laboratory abnormalities will not be recorded on the adverse event CRF pages. Information entered on the adverse event CRF pages will include:

- § Specific type and duration of reaction (i.e., start and stop dates, resolution).
- § Severity/grade.
- § Relationship to study drug (causality, attribution).
- § Management of the event, if treated with medication and other actions taken to alleviate the clinical event.
- Whether or not it was considered a SAE.

A preexisting condition is one that is present at the start of the study. A preexisting condition will be recorded as an adverse event if the frequency, intensity, or the character of the condition worsens during the study period.

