8.1 Adverse Event Reporting Requirements

An adverse experience is defined as any unintended or abnormal clinical observation that is not of benefit to the patient. Either the condition was not present prior to exposure to the study therapy, or it has worsened in intensity or frequency following exposure to the study therapy.

All "unexpected" (defined below) and/or "serious" (defined below) adverse events occurring during the active portion of therapy, or up to 30 days after the last dose of treatment, will be reported to the Office of Human Research Services at [contact]. Events will be promptly reported, in writing, to the local IRB in accordance with IRB policy. If a death occurs the IRB

will be notified within 24-hours of initial receipt of information. All other SAEs must be reported to the IRB within three to ten days of initial receipt of information. Written follow-up reports are required when additional information is needed to fully characterize the event. Copies of each report sent to the IRB will be kept in the study regulatory file.

During the radiation phase of treatment, they are seen weekly by the treating radiation oncologist, who can report any applicable toxicities.

During the 3 weeks of neoadjuvant cetuximab, the patients must still be seen weekly by radiation oncology at either Robert Wood Johnson University Hospital (RWJUH) or Rutgers New Jersey Medical School, in order to evaluate for folliculitis. In this manner, the patients may thus be monitored for toxicity weekly.

Reporting SAEs using commercially available drugs:

In addition, any unexpected (*not listed in the package insert*) serious adverse events that are **associated** (definitely, probably or possibly related) with the use of cetuximab or cisplatin must be reported to the FDA within 10 business days using a FDA Form MedWatch 3500 form <http://www.fda.gov/medwatch/safety/3500.pdf> (fax # [name]).

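### For cetuximab-RT patients, the 30-day adverse event window closes before the protocol's own late death time, electrolyte watch and scheduled chemistry draws

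*Combined protocol and SAP*

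**What the plan says.** - **Recording.** Section 8 covers events "occurring during the active portion of therapy, or up to 30 days after the last dose of treatment will be graded". For laboratory abnormalities, only grade 3-4 goes on the adverse event form.
- **Reporting.** Section 8.1 has unexpected or serious "adverse events occurring during the active portion of therapy, or up to 30 days after the last dose of treatment, will be reported" to OHRS. The same paragraph asks for IRB notice of a death within 24 hours and states no separate time limit for it.
- **Cited deaths.** Section 7.4.3.5 says that cardiopulmonary arrest or sudden death "occurred in 4 (2%) of 208 patients treated with radiation therapy and Erbitux". For the three patients with prior coronary disease: "Death occurred 27, 32, and 43 days after the last dose of Erbitux". For the fourth: "One patient with no prior history of coronary artery disease died one day after the last dose of Erbitux".
- **Electrolytes.** The same section asks for monitoring of hypomagnesemia, "hypocalcemia, and hypokalemia, during and for at least 8 weeks following the completion of Erbitux". It gives severe hypomagnesemia as 6-17% and onset as days to months after starting the drug.
- **Calendar.** The section 6 table draws chemistries in the first 2 months after RT as "X (monthly for two times +- 2 weeks", and again at 3 months (within 1 month). Footnote 1 defines the history visits at 3 months and every 3 months to 2 years: "To include toxicity assessment, ECOG performance status, weight".
- **Missing link.** No section says that findings from those later draws and visits are entered as adverse events.

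**The concern.** The protocol treats sudden death with cetuximab-RT as a risk serious enough to justify an exclusion criterion (5.2.9), and it asks for electrolytes to be followed for two months after the drug. Its adverse event rules stop at 30 days. A site following sections 8 and 8.1 literally could see a grade 3 magnesium value on a draw the protocol ordered and have no instruction to record it. It could also learn of a sudden death at day 43 and have no duty to send it to OHRS as a serious event.

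The only stopping rule (section 16.8) watches progression, so adverse event reporting is a main route by which toxicity becomes visible. Sections 17.5 and 17.6 argue that responders are spared toxicity. A safety record that closes early would tend to flatter that argument.

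**Working it through.** **Inputs.** Death times 1, 27, 32 and 43 days after the last cetuximab dose, 4 of 208 patients (7.4.3.5). Watch of 8 weeks = 56 days (7.4.3.5). Window of 30 days (8, 8.1). 33 fractions (7.3, stated for IMRT). Weekly cetuximab to the end of RT (7.2.6). 27 patients, 60% responding, 16 responders needed (16.2).

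**Plan's own figure.** 4/208 = 1.92%, which rounds to the stated 2%. Cohort size: 0.60 × 27 = 16.2.

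**Step 1: the clock.** The plan does not say whether the last dose means the last drug dose or the last RT fraction. Let g be the days from the last cetuximab dose to the start of the clock. The cutoff, in days after the last cetuximab dose, is c = 30 + g, and the uncovered part of the watch is 56 − c.

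If the clock starts at the last cetuximab dose, g = 0. If it starts at the last fraction, assume five fractions a week without breaks and cetuximab on RT days 1, 8, ..., 43. The 33rd fraction falls on day 45 (Monday to Wednesday start) or day 47 (Thursday or Friday start), so g = 2 or 4. Dosing on another weekday could stretch g to 6.

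| g | cutoff c | deaths after c | watch uncovered |
|---|---|---|---|
| 0 | 30 | days 32, 43 (2 of 4) | 26/56 = 46% |
| 2 | 32 | day 43 (1 of 4) | 24/56 = 43% |
| 4 | 34 | day 43 (1 of 4) | 22/56 = 39% |
| 6 | 36 | day 43 (1 of 4) | 20/56 = 36% |

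Day 43 would come inside only if 30 + g ≥ 43, that is g ≥ 13. Weekly dosing to the end of RT rules that out unless cetuximab is stopped early.

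**Step 2: the draws.** Take a month as 30 days, counted from the end of RT. Month 1 is day 30 ± 14 = days 16-44, so it may fall inside or outside. Month 2 is day 60 ± 14 = days 46-74. Month 3 is day 90, at the earliest 90 − 30 = day 60. Even with the clock at the last fraction, month 2 misses the window by at least 46 − 30 = 16 days. Both later draws are outside on either reading.

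**Step 3: cisplatin cohort.** Count the first cetuximab dose as day 0, so the last neoadjuvant dose is day 14. Assume RT starts on day 21 to 28. The third 3-weekly cisplatin dose is 42 days later, on day 63 to 70. The window then closes on day 93 to 100, which is 79 to 86 days after the last cetuximab dose. That covers all 56 days and every cited death time.

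**Step 4: expected size.** For deaths after day 30 on the drug-dose clock, the rate is 2/208 = 0.96%. Sixteen responders give 16 × 0.0096 = 0.15 expected events and 1 − (1 − 0.0096)^16 = 14% chance of at least one. On the RT clock the rate is 1/208, giving 0.08 expected and 7%. Severe hypomagnesemia is commoner: 16 × 0.06 = 1.0 to 16 × 0.17 = 2.7 patients over the whole course. The protocol gives no timing that would show how many arise after day 30.

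**The case against.** The other side has several good points.

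- A reader might infer that half of the cited deaths are simply outside the window. That holds only if the clock starts at the last cetuximab dose (or RT ends at most a day after it). Section 4.1 counts concurrent RT as active treatment, so the last fraction is a natural reading, and the count is then one of four. This stands.
- A reader might infer that a late death would never reach OHRS or the IRB. The documents do not support that. The 24-hour IRB notice has no time limit of its own, although it sits in the paragraph that sets the 30-day limit and its scope is unclear. Section 13.2 keeps survival in a research chart held at OHRS and updated prospectively. The death would be known, but not necessarily as a serious event. The FDA sentence also has no limit, but it covers only events not listed in the package insert.
- Monitoring patients and recording adverse events are different functions, and section 13.1 ties the eCRFs to the study calendar, so later results may be captured somewhere. That is possible. The gap is that no section links them to the adverse event form.
- A reader might infer that no blood count follows the day-43 cisplatin dose. Counts are weekly during RT and the final RT week extends past that dose, so one may follow.
- The history/toxicity cell for the first 2 months after RT is blank, which invites adding visits and blood counts there. Those would be new procedures, up to 2 × 27 = 54 of each, and closing the recording gap does not require them.
- Toxicity is not a primary or secondary outcome, and the expected number of late deaths is small, more so because 5.2.9 excludes recent cardiac events. This limits the severity, not the finding.

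**Conclusion.** The concern holds for the cetuximab-RT cohort. The window in sections 8 and 8.1 ends before the day-43 death (and the day-32 death on the drug-dose clock), before about 22 to 26 of the 56 watch days, and before the month-2 and month-3 chemistry draws. It does not extend to the cisplatin cohort's cetuximab watch, which its later window already covers.

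This rests on cetuximab continuing weekly to the end of RT, no long breaks, 33 fractions at five a week, 30-day months and, for the cisplatin cohort, the full 3-weekly course. It concerns what must be recorded and reported, not whether anyone would notice the event. No primary result or stopping decision changes. It should be fixed, but it does not threaten the trial's conclusions.

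**What to change.** Reconcile sections 8 and 8.1 with the section 6 calendar and section 7.4.3.5:

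1. Define the last dose as either the last drug dose or the last RT fraction, in the same words in both sections.
2. Run adverse event recording, and serious event and death reporting to OHRS, through the 3-month post-RT visit already scheduled. Even if that visit comes a month early, at about day 60 after RT, it lies beyond day 43 and beyond 56 days from the last cetuximab dose.
3. State that grade 3-4 results from the scheduled post-RT chemistries, and toxicities found at the existing footnote 1 follow-up assessments, go on the adverse event eCRF. This is needed as well as item 2, because a month-2 draw as late as day 74 could follow an early 3-month visit.
4. Say whether the 24-hour IRB death notice is subject to any time limit.

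None of this adds a visit or a blood draw or alters treatment. The cost is protocol wording, somewhat more adverse event and serious event paperwork for about 27 patients, and a less favourable adverse event count.

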8.1 Adverse Event Reporting Requirements

An adverse experience is defined as any unintended or abnormal clinical observation that is not of benefit to the patient. Either the condition was not present prior to exposure to the study therapy, or it has worsened in intensity or frequency following exposure to the study therapy.

All "unexpected" (defined below) and/or "serious" (defined below) adverse events occurring during the active portion of therapy, or up to 30 days after the last dose of treatment, will be reported to the Office of Human Research Services at [contact]. Events will be promptly reported, in writing, to the local IRB in accordance with IRB policy. If a death occurs the IRB

will be notified within 24-hours of initial receipt of information. All other SAEs must be reported to the IRB within three to ten days of initial receipt of information. Written follow-up reports are required when additional information is needed to fully characterize the event. Copies of each report sent to the IRB will be kept in the study regulatory file.

During the radiation phase of treatment, they are seen weekly by the treating radiation oncologist, who can report any applicable toxicities.

During the 3 weeks of neoadjuvant cetuximab, the patients must still be seen weekly by radiation oncology at either Robert Wood Johnson University Hospital (RWJUH) or Rutgers New Jersey Medical School, in order to evaluate for folliculitis. In this manner, the patients may thus be monitored for toxicity weekly.

Reporting SAEs using commercially available drugs:

In addition, any unexpected (*not listed in the package insert*) serious adverse events that are **associated** (definitely, probably or possibly related) with the use of cetuximab or cisplatin must be reported to the FDA within 10 business days using a FDA Form MedWatch 3500 form <http://www.fda.gov/medwatch/safety/3500.pdf> (fax # [name]).

8.2 Definition of Serious Adverse Events (SAEs)

A serious adverse event (experience) is one occurring at any dose level that results in any of the following outcomes:

- § Death
- § Life-threatening- immediate risk of death from the reaction.
- § Requires inpatient hospitalization or prolongation of existing hospitalization.
- § Results in persistent or significant disability/incapacity.
- § Results in a congenital anomaly/birth defect.
- § Requires intervention to prevent one of the outcomes listed in this definition.

The definition of serious adverse event (experience) also includes *important medical events*. Medical and scientific judgment will be exercised in deciding whether expedited reporting is appropriate in other situations, such as important medical events that may not be immediately life-threatening or result in death or hospitalization but may jeopardize the patient or may require intervention to prevent one of the other outcomes listed in the definition above. These events will usually be considered serious. Examples of such events are intensive treatment in an emergency room or at home for allergic bronchospasm; blood dyscrasias or convulsions that do not result in hospitalization.

8.3 Definition of Related

There is a reasonable possibility that the drug caused the adverse experience. That is, the event is judged by the investigator to be possibly, probably or definitely related to the treatment.

8.4 Definition of Unexpected

Any adverse drug experience and/or specificity, that is not included in the current investigator's brochure and/or package insert.

9. Treatment Evaluation/Criteria for Response

For the purposes of this study, the response to neoadjuvant cetuximab is judged by 1) development of cetuximab related folliculitis as below and 2) response at the primary site and neck by CT using RECIST 1.1 criteria.

Response and progression will be evaluated in this study using the international criteria proposed by the Response Evaluation Criteria in Solid Tumors (RECIST 1.1) Committee [JNCI 92(3): 205-216, 2000]. Changes in only the largest diameter (unidimensional measurement) of the tumor lesions are used in the RECIST 1.1 criteria. Note: Lesions are either measurable or non-measurable using the criteria provided below. The term "evaluable" in reference to measurability will not be used because it does not provide additional meaning or accuracy.

In addition, patients will be evaluated weekly during neoadjuvant cetuximab to assess for grade of rash using CTCAE 4.0 criteria.

9.1 Evaluation of folliculitis

Folliculitis will be graded weekly following the initiation of neoadjuvant cetuximab per the criteria in section 7.2.3.1

9.2 Evaluation of CT response at primary site and neck

CT scans of the neck with IV contrast will be taken before and after neoadjuvant cetuximab (Day 14-21 after the first dose of cetuximab). At the primary site and neck lymph nodes, the largest diameter on axial CT slices will be measured and recorded. All measurements will be taken and recorded in metric notation using measuring software in the applicable radiology programs. In all possible cases, spiral CT (as opposed to standard CT) will be performed. Response will be graded per RECIST 1.1 criteria: [E.A. Eisenhauer et al. New response evaluation criteria in solid tumours: Revised RECIST 1.1 guideline (version 1.1). Eur J Cancer 45 (2009) 228-247].

Evaluation of Target Lesions

| | |
|---------------------------|---|
| Complete Response (CR): | Disappearance of all target lesions. Any pathological lymph nodes (whether target or non-target) must have reduction in short axis to <10 mm. |
| Partial Response (PR): | At least a 30% decrease in the sum of diameters of target lesions, taking as reference the baseline sum diameters. |
| Progressive Disease (PD): | At least a 20% increase in the sum of diameters of target lesions, taking as reference the smallest sum on study (this includes the baseline sum if that is the smallest on study). In addition to the relative increase of 20%, the sum must also demonstrate an absolute increase of at least 5 mm. (Note: the appearance of one or more new lesions is also considered progression). |
| Stable Disease (SD): | Neither sufficient shrinkage to qualify for PR nor sufficient increase to qualify for PD, taking as reference the smallest sum diameters while on study |

Please note that significant changes from version 1.0 include for malignant lymph nodes: To be considered pathologically enlarged and measurable, a lymph node must be >15mm in short axis when assessed by CT scan (CT scan slice thickness recommended to be no greater than 5 mm). At baseline and in follow-up, only the short axis will be measured and followed.

10. Removal of Patients from Study/Off Study Criteria

In the absence of treatment delays due to adverse events, treatment may continue until one of the following criteria applies:

- a) Intercurrent illness that prevents further administration of treatment,
- b) Patient decides to withdraw from the study,
- c) Noncompliance with treatment plan,
- d) General or specific changes in the patient's condition render the patient unacceptable for further treatment in the judgment of the investigator
- e) Protocol violation - any patient found to have entered this study in violation of the protocol might be discontinued from the study at the discretion of the Principal Investigator.

11. Laboratory Evaluations and Procedures/Correlative and Pharmacokinetic Studies

11.1 An overview of the possible molecular investigations, and in order of priority include

1. FoundationOne genomic profile from paraffin embedded tumor samples taken before cetuximab or after locoregional/distant failure
2. RNA sequencing of tumor samples before and after cetuximab
3. RNA sequencing of skin samples before and after cetuximab
4. DNA sequencing of tumor and skin samples before and after cetuximab
5. IHC analysis of EGFR downstream pathways that are illuminated by the above

The laboratory investigations are very comprehensive, ranging from partial DNA sequencing (FoundationOne™ (or other certified genomic analysis facility)) in order to check for a battery of known DNA mutations related to cancer, to RNA sequencing on fresh tissue, which will shed light on how protein production is altered when the tumor is treated with cetuximab. FoundationOne™ (or other certified genomic analysis facility) is targeted DNA sequencing that is performed on paraffin embedded tumor samples. As a pan-cancer test, FoundationOne™ (or other certified genomic analysis facility) is designed to interrogate the entire coding sequence of 236 cancer-related genes (3,769 exons) plus 47 introns from 19 genes often rearranged or altered in cancer. These genes are known to be somatically altered in human solid cancers based on recent scientific and clinical literature.^{32 33} In addition, RNA sequencing will be performed on tumor samples from before and after neoadjuvant cetuximab, to investigate changes in protein production caused by cetuximab ie changes in protein production downstream in the EGFR pathway or completely alternate pathways that may be triggered by cetuximab. In addition, HPV status can be easily determined from RNA sequencing. Once the cDNA library is created by Cancer Institute of New Jersey Functional Genomics ([name]), analysis will be performed by Cancer Institute of New Jersey bioinformatics ([name]).

